12.2.2 Other Outcome Types

Outcomes with a baseline measurement and only a single post-baseline measurement can be analysed by ANCOVA, with treatment arm as the explanatory variable, and baseline value as an adjusting covariate if the above model approach is unsuitable.

Dichotomous outcomes (e.g. incidence of adverse events, or response) will be analysed by Fisher's exact test, with treatment arm as the explanatory variable.

Safety data will be presented in tabular and/or graphical format and summarized descriptively according to appropriate standards.

Key pharmacodynamics/biomarker outcome measures (expression of blood or serum and faecal biomarkers, e.g. IFN-γ, CRP, IL6, Calprotectin) and serum level of IP10, total and free IL-18 will be descriptively and/or graphically summarized as appropriate.

The presence or absence of antibodies to GSK1070806 will be descriptively and/or graphically summarised as appropriate to the data.

Full details will be included in the Statistical Analysis Plan.

Analysis of SES-CD will be adjusted to take account of baseline value.

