2.5 Further Secondary Outcome Measures (Non-Hierarchical)

- 1. Serum concentrations of GSK1070806 over time and derived PK parameters if feasible AUC(0- τ), Cmax, Tmax and t½.
- 2. Abdominal pain (AP) over time (refer to Schedule of Events for assessment times).
- 3. Stool frequency (SF) over time (refer to Schedule of Events for assessment times).
- 4. Post-treatment (w12) SES-CD endoscopic score.
- 5. Proportion of patients in clinical remission defined as average daily Stool Frequency \leq 2.8 and /or average daily Abdominal pain \leq 1 and CDAI <150.

- Kinetics of induction of clinical response defined as a ≥ 70 point decrease from baseline CDAI score (or score ≤ 150).
- 7. Serum C-reactive protein over time (refer to Schedule of Events for assessment times).
- 8. Faecal calprotectin over time (refer to Schedule of Events for assessment times).
- 9. Incidence and titers of serum of anti-GSK1070806 antibodies before and after GSK1070806 administration.

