12. STATISTICAL CONSIDERATIONS

The proposed analysis methods are described in Section 12.2. Success of the trial with respect to CDAI score will be defined as concluding that the mean response profile under GSK1070806 is superior (i.e. takes lower values) to that under placebo. This repeated measures analysis will be performed using a regression model. The determination of success is not attached to any particular time-point, but considers outcomes at all times. Secondary outcome measures will provide supportive evidence for the effect of GSK1070806 in patients with active CD.

Up to 21 patients will be randomised to GSK1070806 or placebo in a 2:1 ratio. The sample size has been chosen based on feasibility and practical constraints. This trial was initially conceived using a sample size of at least 30 patients. An indication of the statistical performance of the trial with n=30 using the proposed analysis method is given in Section 12.3.

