12.3.1 Simulating CDAI paths for patients in a scenario

- 1) Baseline values of CDAI score for patients allocated to placebo and GSK1070806 are randomly sampled from a Normal (285, 80²) distribution. Thus, baseline CDAI scores are centred at 285 and 95% of values are in the approximate interval (125, 445).
- 2) Vectors of treatment-effects at weeks (0, 2, 4, 8, 12, 16, 24) are selected for placebo, $\lambda_P(t)$, and GSK1070806, $\lambda_E(t)$. These reflect the value of the mean CDAI path through time as a multiple of the baseline value. Values less then 1 show improvement, i.e. falling CDAI scores. The chosen subscripts are *P* for placebo and *E* for experimental treatment.
- 3) The value at time t of the CDAI path for a patient with baseline score y_0 allocated to treatment A is

$$y_0 * \lambda_A(t) + \epsilon$$

where ε is a noise term, distributed N(0, 30²). For instance, if a patient has y₀ = 300, is allocated to GSK1070806 with $\lambda_{E}(t) = 0.9$, and happens to take $\varepsilon = 12$ at time *t*, then for that patient:

CDAID

The mean baseline value and variability of baseline scores were selected to mimic those reported in a recentlypublished randomised controlled trial (RCT) of CD: (Zhang, Lv et al. 2018). Under the described method, the variability of CDAI scores are driven by the variability of the baseline scores and the noise terms. The variance of the noise, 302, was chosen by trial-and-error so that the overall variability of the CDAI scores approximately matched those at the time horizons reported in [Zhang et al. 2017].

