12.3.2 Reaching a trial decision in simulations

In simulations, we analyse outcomes using the model

$$y_{ij} = \alpha + a_i + \beta_j + \gamma_j z_i + \epsilon_{ij}$$

where:

- y_{ij} is the CDAI value of patient *i* at time t_{j} ;
- *α* is the mean baseline CDAI value across both arms;
- a_i is the random effect for the baseline CDAI score for patient *i*;
- β_i is the fixed placebo effect at time t_i ;
- γ_i is the fixed effect of the experimental drug over placebo at time t_i ;
- z_i takes the value 1 for patients allocated to GSK1070806, else 0;
- ϵ_{ij} is the noise time for patient *i* at time t_{j} ;
- $a_i \sim N(0, \sigma_a^2)$
- $\epsilon_{ii} \sim N(0, \sigma^2)$

The presence of a treatment effect is formally tested by the hypothesis:

$$\gamma_1 = \gamma_2 = \dots = \gamma_j = 0$$

The presence of aggregate treatment benefit is tested via the supplemental requirement that:

$$\sum_j \gamma_j < 0$$

We present in the following sections the performance of these combined criteria, fitting mixed effects models by REML using the nlme package in R, interpreting p-values less than 0.05 as being significant.

It should be noted that the analysis method in this section does not reflect exactly our proposal for the trial. As noted above, we propose to use the Bayesian analogue to this method with informative priors on the placebo effects. This extra information should increase the ability of the model to distinguish between the paths by arm, without unduly increasing the false positive rate. Furthermore, we would hope to model the CDAI paths using smooth functions of time (for instance, polynomials). These would require fewer parameters than the saturated model above. This would hopefully improve statistical performance as well.

12.3.3 Scenario 1

In this null scenario, we assume that the placebo effect is positive but very small, and that GSK1070806 is assumed to have no effect on CDAI beyond placebo effect. The values of $\lambda P(t)$ and $\lambda E(t)$ are identical, given in column A of Table 10. The expected change from baseline is shown in column G. A single trial simulation using n1 = 10 placebo paths and n2 = 20 experimental paths is shown in Figure 4. We see that the mean lines are colocated and the confidence intervals largely overlap. This is the null scenario. The probability of approving GSK1070806 in this scenario is approximately 3.1%.

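### Fisher's exact test for response at 14 v 7 is valid but has a true size of at most 2.2%; Boschloo's test would add about 10-15 points of power for week-12 response under the protocol's own CDAI scenarios, and much less for remission or at some nearby arm sizes

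*Protocol*

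**What the plan says.** Section 12.2.2 assigns dichotomous outcomes, giving adverse-event incidence and response as its examples, to Fisher's "exact test, with treatment arm as the explanatory variable". Section 12 gives the size: "Up to 21 patients will be randomised to GSK1070806 or placebo in a 2:1 ratio". That is 14 active and 7 placebo if recruitment is complete and exactly balanced.

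A significance level appears only in section 12.3.2, for the CDAI simulations ("interpreting p-values less than 0.05 as being significant"). No level, sidedness, expected rate or power is given for any dichotomous outcome.

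The efficacy outcomes concerned are in section 2.5. One is "Kinetics of induction of clinical response defined as a ≥ 70 point decrease from baseline CDAI score (or score ≤ 150"). Another is remission, which opens "Proportion of patients in clinical remission defined as average daily Stool Frequency" and also requires CDAI below 150. Endoscopic response is an exploratory measure in section 2.7. Section 12 describes the role of the secondary measures: "Secondary outcome measures will provide supportive evidence for the effect of GSK1070806 in patients with active CD".

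**The concern.** With 14 and 7 patients there are only 15 × 8 = 120 possible tables. Fisher's test conditions on the total number of responders, so within each total its attainable p-values are few and the nominal 5% is mostly unused. An unconditional test that ranks tables by the same Fisher p-value, but sets the cut-off so that the true size stays within 5% for every common rate, can reject in more tables without exceeding the permitted error rate. That test is Boschloo's.

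The binary efficacy results are meant to support the CDAI analysis. The sample was set by feasibility and reduced from 30 to 21, so power cannot easily be recovered by recruiting more patients. A change of test costs no patients.

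**Working it through.** The protocol gives no performance figure for the binary tests, so there is none to reproduce first.

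**Inputs.** Arms of 14 and 7 (section 12). Two-sided 5% (assumed). Response and remission definitions (section 2.5). CDAI model (section 12.3.1): baseline "randomly sampled from a Normal (285, 80²) distribution", week-12 value = baseline × λ + noise with SD 30. Week-12 λ from Table 10: placebo 0.98 in scenarios 2-4 and 0.85 in scenario 5; active 0.78, 0.83, 0.81 and 0.70 in scenarios 2-5.

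**Step 1: size.** For a rejection region R and rates p_E, p_P, the rejection probability is the sum over tables (a, b) in R of Bin(a; 14, p_E) × Bin(b; 7, p_P). Size is its maximum over p_E = p_P.
- Fisher, p ≤ 0.05: maximum 2.21%, at a common rate near 0.40. It is 0.70% at a rate of 0.10, 1.54% at 0.20 and 2.06% at 0.30.
- Boschloo: the critical Fisher p is 0.0877 and the maximum size is 4.75%. No table rejected by Fisher is dropped.

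**Step 2: which results change.** Four tables favouring active are added: 6/14 v 0/7 (Fisher p = 0.061), 9/14 v 1/7 (0.064), 11/14 v 2/7 (0.056) and 13/14 v 4/7 (0.088). Their observed differences run from 36 to 50 points. As a check on the first, the table counts at or below the observed one are C(14,6) = 3003, C(7,5) × 14 = 294 and 7, out of C(21,6) = 54264. So p = 3304/54264 = 0.061.

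**Step 3: response rates implied by the protocol's model.** A patient responds if the week-12 value is at or below the larger of (baseline − 70) and 150. The rate is therefore the mean over baseline y₀ of Φ((max(y₀ − 70, 150) − λy₀)/30).

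| Scenario | Active v placebo | Fisher power | Boschloo power | Gain (points) |
|---|---|---|---|---|
| 2 | 51% v 7% | 40.4% | 55.1% | 14.7 |
| 3 | 34% v 7% | 10.2% | 20.7% | 10.5 |
| 4 | 41% v 7% | 20.0% | 33.8% | 13.7 |
| 5 | 75% v 28% | 41.1% | 53.4% | 12.4 |

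Gains are taken before rounding.

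**Step 4: where the gain is smaller.**
- 20-point differences (assumed rates, placebo v active): 10% v 30%, 4.6% to 10.9%; 20% v 40%, 7.2% to 13.2%. Both gains are about 6 points.
- Week-12 remission, using only the CDAI < 150 part: rates of 12-22% active v 6-11% placebo, Fisher power 0.2-1.0%, gain 0.4-2.4 points. The largest week-24 gain is 4.3 points, in scenario 5.
- Other arm sizes, over five assumed pairs (placebo v active 10% v 40%, 10% v 50%, 20% v 60%, 30% v 70%, 20% v 70%). At 14 v 7 the gains are 11.5-13.6 points. At 13 v 8 they are 2.5-8.1, at 15 v 6 they are 1.0-10.4, and at 12 v 7 they are 1.6-8.5. Fisher's maximum size in these three layouts is about 3%. At 13 v 7 it is 2.1% and the gains are 10.4-15.5.
- Another unconditional test: Z-pooled Barnard gains 4.5, 0.6, 1.5 and 11.6 points over Fisher in scenarios 2-5.

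**The case against.** Fisher's test is standard and valid, and section 12.2.2 leaves full details to a statistical analysis plan. Section 12.2.1 intends a Bayesian model for CDAI and other clinical efficacy outcomes, so Fisher's test may not be the only efficacy comparison. Trial success is defined on the CDAI profile. Clinical response is listed as kinetics, and as time to response, rather than as one week's proportion. On this view, preferring one valid exact test to another is a matter of taste.

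Much of this stands, and it fixes the point as an efficiency suggestion. It does not remove the point. The choice of test is stated, response is named under it, and Boschloo's test is never less powerful at the same level.

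Three stronger readings are tempting, and the documents support none of them:
- A reader might infer that type I error is uncontrolled. It is controlled, conservatively.
- A reader might infer a fixed loss of around 10 points or more for response and remission alike. The protocol states no binary rates, and its own model puts remission so low that both tests have almost no power.
- A reader might infer that any unconditional exact test recovers the loss, or that over half the error rate is always discarded. The Z-pooled result and the sizes near 3% at neighbouring arm sizes contradict both.

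**Conclusion.** The point holds as a cheap improvement. At exactly 14 v 7 and two-sided 5%, Fisher's test uses at most 2.2 of the 5 percentage points available, and Boschloo's test dominates it. For week-12 clinical response the gain is about 10-15 points of power under scenarios 2-5. It is about 6 points for 20-point differences, about 1-10 at several nearby arm sizes, and under about 2.5 for week-12 remission.

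This rests on the assumed level and sidedness, complete and exactly balanced recruitment, the CDAI simulation model for the rates, response taken as a week-12 proportion, and remission reduced to its CDAI part. The comparisons are supportive, or exploratory for endoscopic response, and the main CDAI conclusion is not affected.

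**What to change.** In section 12.2.2, before unblinding, name Boschloo's unconditional exact test in place of Fisher's for between-arm comparisons of efficacy proportions: clinical response, remission and, as exploratory, endoscopic response. State the level and sidedness. Report the risk difference with an exact unconditional 95% interval. Compute the critical region at the arm sizes actually analysed. Adverse-event comparisons can stay as they are.

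The cost is a wording change; standard software exists, and no extra patients or visits are needed. The downside is a less familiar test, and some readers prefer conditional inference.

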12.3 Justification of Sample Size

The sample size is justified here with respect to the key secondary outcome measure, CDAI score. In a repeated measures study, efficacy may manifest at a variety of assessment times. In the early phase setting, we do not know when efficacy will manifest. Thus, we seek an analysis method that will be flexible enough to detect efficacy, regardless of the time horizon. As such, we demonstrate statistical performance using simulation in a small number of indicative scenarios with differing response profiles. The scenarios are detailed in sections below, and summarised in Table 10. The method of simulating patient CDAI paths is described in Section 12.3.1 and reaching a trial decision in Section 12.3.2.

12.3.1 Simulating CDAI paths for patients in a scenario

- 1) Baseline values of CDAI score for patients allocated to placebo and GSK1070806 are randomly sampled from a Normal (285, 80²) distribution. Thus, baseline CDAI scores are centred at 285 and 95% of values are in the approximate interval (125, 445).
- 2) Vectors of treatment-effects at weeks (0, 2, 4, 8, 12, 16, 24) are selected for placebo, $\lambda_P(t)$, and GSK1070806, $\lambda_E(t)$. These reflect the value of the mean CDAI path through time as a multiple of the baseline value. Values less then 1 show improvement, i.e. falling CDAI scores. The chosen subscripts are *P* for placebo and *E* for experimental treatment.
- 3) The value at time t of the CDAI path for a patient with baseline score y_0 allocated to treatment A is

$$y_0 * \lambda_A(t) + \epsilon$$

where ε is a noise term, distributed N(0, 30²). For instance, if a patient has y₀ = 300, is allocated to GSK1070806 with $\lambda_{E}(t) = 0.9$, and happens to take $\varepsilon = 12$ at time *t*, then for that patient:

CDAID

The mean baseline value and variability of baseline scores were selected to mimic those reported in a recentlypublished randomised controlled trial (RCT) of CD: (Zhang, Lv et al. 2018). Under the described method, the variability of CDAI scores are driven by the variability of the baseline scores and the noise terms. The variance of the noise, 302, was chosen by trial-and-error so that the overall variability of the CDAI scores approximately matched those at the time horizons reported in [Zhang et al. 2017].

12.3.2 Reaching a trial decision in simulations

In simulations, we analyse outcomes using the model

$$y_{ij} = \alpha + a_i + \beta_j + \gamma_j z_i + \epsilon_{ij}$$

where:

- y_{ij} is the CDAI value of patient *i* at time t_{j} ;
- *α* is the mean baseline CDAI value across both arms;
- a_i is the random effect for the baseline CDAI score for patient *i*;
- β_i is the fixed placebo effect at time t_i ;
- γ_i is the fixed effect of the experimental drug over placebo at time t_i ;
- z_i takes the value 1 for patients allocated to GSK1070806, else 0;
- ϵ_{ij} is the noise time for patient *i* at time t_{j} ;
- $a_i \sim N(0, \sigma_a^2)$
- $\epsilon_{ii} \sim N(0, \sigma^2)$

The presence of a treatment effect is formally tested by the hypothesis:

$$\gamma_1 = \gamma_2 = \dots = \gamma_j = 0$$

The presence of aggregate treatment benefit is tested via the supplemental requirement that:

$$\sum_j \gamma_j < 0$$

We present in the following sections the performance of these combined criteria, fitting mixed effects models by REML using the nlme package in R, interpreting p-values less than 0.05 as being significant.

It should be noted that the analysis method in this section does not reflect exactly our proposal for the trial. As noted above, we propose to use the Bayesian analogue to this method with informative priors on the placebo effects. This extra information should increase the ability of the model to distinguish between the paths by arm, without unduly increasing the false positive rate. Furthermore, we would hope to model the CDAI paths using smooth functions of time (for instance, polynomials). These would require fewer parameters than the saturated model above. This would hopefully improve statistical performance as well.

12.3.3 Scenario 1

In this null scenario, we assume that the placebo effect is positive but very small, and that GSK1070806 is assumed to have no effect on CDAI beyond placebo effect. The values of $\lambda P(t)$ and $\lambda E(t)$ are identical, given in column A of Table 10. The expected change from baseline is shown in column G. A single trial simulation using n1 = 10 placebo paths and n2 = 20 experimental paths is shown in Figure 4. We see that the mean lines are colocated and the confidence intervals largely overlap. This is the null scenario. The probability of approving GSK1070806 in this scenario is approximately 3.1%.

Figure 4 - $n_1 = 10$ placebo paths and $n_2 = 20$ experimental paths summarised by loess smoothers, plus bootstrapped 95% confidence intervals of the mean process value.

12.3.4 Scenario 2

In this active scenario, GSK1070806 is assumed to have a large and progressive effect on CDAI until week 12, where the experimental response curve plateaus. Patients allocated to placebo are assumed to respond as described in Scenario 1, i.e. with a positive but very small effect. The values of $\lambda P(t)$ are given in column A and $\lambda E(t)$ in column B of Table 10. The expected changes from baseline are shown in columns G and H. A single trial simulation using n1 = 10 placebo paths and n2 = 20 experimental paths is shown in Figure 5. We see that the mean lines are quite distinct, although the confidence intervals do not truly separate. Despite this, the power garnered from analysing the outcomes over all time-horizons simultaneously means that the probability of approving GSK1070806 in this scenario is approximately 92.8%.

Figure 5 - $n_1 = 10$ placebo paths and $n_2 = 20$ experimental paths summarised by loess smoothers, plus bootstrapped 95% confidence intervals of the mean process value.

12.3.5 Scenario 3

In this active scenario, GSK1070806 is assumed to have a strong (albeit weaker than scenario 2) and progressive effect on CDAI until week 16, where the expected response curve plateaus. Patients allocated to placebo are assumed to respond as described in Scenario 1. The values of $\lambda P(t)$ are given in column A and $\lambda E(t)$ in column C of Table 10. The expected changes from baseline are shown in columns G and I. A single trial simulation using n1 = 10 placebo paths and n2 = 20 experimental paths is shown in Figure 6. We see that the mean lines are quite distinct, and that the confidence intervals scarcely separate. Again, despite this, the power garnered from analysing the outcomes over all time-horizons simultaneously means that the probability of approving GSK1070806 in this scenario is approximately 86.0%. The weight of evidence supporting a difference in response curves could be loosely interpreted as correlating with the area between the two curves. The probability of approval is lower here than in scenario 2 because that area is smaller.

Figure 6 - $n_1 = 10$ placebo paths and $n_2 = 20$ experimental paths summarised by loess smoothers, plus bootstrapped 95% confidence intervals of the mean process value.

12.3.6 Scenario 4

In this active scenario, GSK1070806 is assumed to have a strong (albeit weaker than scenario 2) and progressive effect on CDAI until week 12, where the expected response curve plateaus. Patients allocated to placebo are assumed to respond as described in Scenario 1. The values of $\lambda P(t)$ are given in column A and $\lambda E(t)$ in column D of Table 10. The expected changes from baseline are shown in columns G and J. A single trial simulation using n1 = 10 placebo paths and n2 = 20 experimental paths is shown in Figure 7. We see that the mean lines are quite distinct, and that the confidence intervals never separate. The probability of approving GSK1070806 in this scenario is approximately 85.1%.

Figure 7 - $n_1 = 10$ placebo paths and $n_2 = 20$ experimental paths summarised by loess smoothers, plus bootstrapped 95% confidence intervals of the mean process value.
12.3.7 Scenario 5

Hitherto, we have used weak placebo effects. In a recent placebo-controlled RCT in CD (Sandborn, Lee et al. 2017)], large falls in CDAI and a high response rate were observed in patients on placebo and experimental drug alike. More generally, a meta-analysis of placebo response rates showed that responses to placebo are common and often large (Su, Lichtenstein et al. 2004). In this scenario, we assume that placebo are strong, and that responses to GSK1070806 are stronger still. The values of $\lambda P(t)$ are given in column E and $\lambda E(t)$ in column F of Table 10. The expected changes from baseline are shown in columns K and L. A single trial simulation using n1 = 10 placebo paths and n2 = 20 experimental paths is shown in Figure. The probability of approving GSK1070806 in this scenario is approximately 88.0%.

Figure 8 - n1 = 10 placebo paths and n2 = 20 experimental paths summarised by loess smoothers, plus bootstrapped 95% confidence intervals of the mean process value

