12.2 Analysis of Outcome Measures

12.2.1 Outcomes with Repeated Measures

Outcomes with repeated measures (i.e. those with at least two post-baseline measurements, such as CDAI) will be analysed by hierarchical models. Terms will be included to reflect the effects of assessment time, the interaction of treatment arm with assessment time, and baseline heterogeneity in patients. Inference on the effect of GSK1070806 with respect to an outcome measure will be made by assessing the necessity of the treatment arm variables in modelling the mean outcome paths by trial arm, i.e. investigating if the mean outcome paths diverge. Smooth functions of time will be used in the modelling where they can be justified by the data, but a fully-specified model with estimates of treatment effects in each arm at each time-point will be used if smooth functions are not appropriate. Further model features, such as specialised covariance structures will be considered as necessitated by the data. The estimated mean difference between treatment arms through time will be reported with appropriate estimates of variability. Demonstrations of the proposed analysis method with respect to CDAI are given in Section 12.3.1.

It is our intention to use a Bayesian implementation of the above method to compare CDAI outcomes (and other clinical efficacy outcomes) under GSK1070806 and placebo. We propose to use moderately informative priors on the expected outcomes of patients allocated to placebo. These will be justified using published studies where placebo was used and CDAI was assessed in patients with CD. Priors with mean zero will be used for the mean response to experimental drug in excess of placebo effect. This will allow us to preferentially randomise to the experimental therapy, whilst maintaining statistical performance in a manner consistent with published data.

CDAID

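### The simulated CDAI success rule does not control the error of its superiority claim: harm can pass if baseline is left unadjusted, and crossing paths can pass either way

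*Protocol*

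**What the plan says.** Section 12 of the protocol states: "Success of the trial with respect to CDAI score will be defined as concluding that the mean response profile under GSK1070806 is superior", and explains superior as taking lower values, judged over all visits. Section 12.2.1 bases inference on whether the treatment terms are needed in the model, that is on "investigating if the mean outcome paths diverge".

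Section 12.3.2 gives the rule used in the simulations. It has two parts:

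- "The presence of a treatment effect is formally tested by the hypothesis" that every treatment effect γ_j is zero, "interpreting p-values less than 0.05 as being significant".
- "The presence of aggregate treatment benefit is tested via the supplemental requirement that" the sum of the γ_j is below zero. No standard error, threshold or p-value is attached.

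In the same section, α is the baseline mean over both arms and γ_j is the drug effect over placebo at time t_j. The section adds that the trial itself will use a Bayesian analogue with informative placebo priors. The only inactive scenario simulated is Scenario 1, with identical paths, approved 3.1% of the time.

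**The concern.** The claim has a direction, but the only part of the rule with an error rate does not. The joint test can reject because CDAI falls, rises, or does one and then the other. Direction is left to the sign of an estimated sum, however noisy that sum is. Scenario 1 cannot expose this, because with identical paths the joint test seldom rejects.

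The untested profiles are not far-fetched here. Sections 1.1.5 and 1.1.8 report conflicting evidence on whether blocking IL-18 protects or harms the gut. Section 1.2.3 predicts gut IL-18 suppression for 90 days after one dose, while CDAI is followed to week 24. Section 12.3 says it is not known when efficacy will appear. A superiority conclusion could therefore be drawn for a drug that worsens CDAI, or that helps early and harms late.

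**Working it through.** **Inputs.** From Section 12.3.1: baselines are "randomly sampled from a Normal (285, 80²) distribution", visit noise has SD 30, and visits are at weeks 0, 2, 4, 8, 12, 16 and 24. Scalars are from Table 10. The simulated size is 10 placebo and 20 active. The current size is 21 at 2:1 (Section 12), so 7 and 14.

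**1. Reproduce Table 10 (n=30).** Random-intercept model, F test at 0.05, plus the sign condition on the six post-dose γ:

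| Version | Sc 1 | Sc 2 | Sc 3 | Sc 4 | Sc 5 |
|---|---|---|---|---|---|
| Stated | 0.031 | 0.928 | 0.860 | 0.851 | 0.880 |
| Arm difference free at all 7 visits, week 0 without noise | 0.031 | 0.926 | 0.860 | 0.847 | 0.881 |
| Common baseline | 0.03 | 0.999 | 0.995 | 0.976 | 0.962 |

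The stated figures match the free week-0 version. The common-baseline version, which is how the model text reads, does not give them.

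**2. Why harm can pass in the free week-0 version.** Take the mirror of Scenario 3 at n=21.

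- Column C minus column A: −0.02, −0.04, −0.09, −0.15, −0.20, −0.20, sum −0.70. Mirrored, the true sum of γ is +0.70 × 285 = +199.5.
- Post-dose scalars sum to 5.90 on placebo and 5.90 + 0.70 = 6.60 on active.
- Var(sum) = 80² × (5.90²/7 + 6.60²/14) + 6 × 30² × (1/7 + 1/14) = 51,739 + 1,157 = 52,896, so SD = 230.
- P(estimated sum < 0) = Φ(−199.5/230) = Φ(−0.867) = 0.193.

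Baseline imbalance contributes 51,739/52,896 = 98% of that variance. The joint test draws on within-patient change and usually rejects, so approval comes close to this ceiling of 19%.

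**3. Harm at every post-dose visit (simulated approval, free week-0 version).**

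| Mirror of | Sc 2 | Sc 3 | Sc 4 | Sc 5 |
|---|---|---|---|---|
| n=30 | 9.1% | 14.5% | 12.8% | 8.7% |
| n=21 | 12.0% | 16.8% | 13.2% | 10.4% |

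Separate runs extend the n=21 range to 19%. Half-size mirrors of Scenarios 2-4 give 8-12% (n=30) and 6-9% (n=21). With a common baseline and the same sign check, full mirrors are approved about 0% of the time, and at most 0.7% if week 0 also carries noise. Half-size mirrors reach 1.8% at n=21 with a noisy week 0.

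**4. Crossing paths with zero net effect (assumed profiles).** If the true sum is zero, approval is roughly P(joint test rejects) × 1/2, so it climbs towards 50%.

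- Differences −d, −d, −d/3, +d/3, +d, +d: about 10% at d=10, 26-38% at d=20, 43-50% at d=30, over both sample sizes and separate runs.
- A flatter shape (−d at weeks 2-8, +d at weeks 12-24): 29% and 20% (n=30, n=21) at d = 0.05 × 285 = 14 points; 46% and 39% at 0.075 × 285 = 21 points.
- The flatter shape under a common baseline, d from 14 to 57 points: 31-50% (n=30) and 23-50% (n=21). Baseline handling does not cure this part.

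**5. Power with a common baseline, sign check unchanged (n=21, Scenarios 2-5).**

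| | Free week 0 | Common baseline |
|---|---|---|
| Week 0 without noise | 0.86 / 0.78 / 0.70 / 0.69 | 0.97 / 0.95 / 0.86 / 0.81 |
| Week 0 with SD-30 noise | 0.80 / 0.72 / 0.62 / 0.58 | 0.91 / 0.88 / 0.76 / 0.66 |

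**6. Adding a directional test.** Common baseline, joint test, and sum below zero with z < −1.96: crossing profiles fall to about 0-2% and harm to 0%. Power at n=21 is 0.97/0.82/0.80/0.78 without week-0 noise and 0.82/0.62/0.61/0.62 with it.

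**The case against.** **This is the simulation rule, not the trial's rule.** Section 12.3.2 says so, no Bayesian decision threshold appears in the protocol, and Section 12.2.2 leaves full details to the SAP. Section 12.2.1 also promises the mean difference over time with its variability, so a harmful or crossing profile would be visible. This stands, and it lowers the severity. It does not remove the point: the trial method is described as the analogue of this one, and every performance figure offered rests on this rule.

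**A reader might infer that any drug with no net benefit is approved 30-50% of the time.** The protocol does not support that. No effect at any visit gives 3%. Rates of that order need crossings of about 20-30 points in the graded shape, or somewhat less in the flatter one, and the protocol posits neither.

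**A reader might blame the sign check alone for the harm approvals.** It is not the sole cause. The same check with a common baseline approves full-mirror harm 0-1% of the time, so those approvals come from unadjusted baseline imbalance.

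**A reader might conclude that a single baseline-adjusted test of the post-dose mean beats the stated rule everywhere.** That holds only if week-0 CDAI has no noise. With noise it loses in Scenario 3 (n=21: 0.64 against 0.73). At exchangeable correlation 0.7 the Scenario 3 loss is larger (0.36-0.38 against 0.48-0.55). Section 12.3 deliberately seeks efficacy at any time horizon, so replacing the joint test is partly a trade-off.

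**Conclusion.** The concern holds in a limited form. The rule in Section 12.3.2 does not control the error of the directional claim in Section 12, for two separate reasons. First, in the version that reproduces Table 10, chance baseline imbalance drives the sign of the sum, and mirror-image harm is approved about 9-15% of the time at n=30 and 10-19% at n=21. Second, under either baseline handling, zero-net crossing profiles are approved at a rate that rises with the crossing, up to 50%.

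These figures rest on the protocol's own data generator and on assumed mirrored and crossing profiles. That week 0 was left free is inferred from the match with Table 10; the protocol does not say it. The change should be made, but it is not critical: CDAI is a key secondary outcome in a phase Ib/IIa trial whose primary objective is safety.

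**What to change.** 1. In Section 12.3.2 and in the Bayesian analogue, estimate the γ_j with a common baseline or with baseline as a covariate, and say which. This uses data already collected. Under the protocol's generator it takes full-mirror harm to about 0-1% and raises power in Scenarios 2-5, with or without week-0 noise.
2. In Sections 12 and 12.3.2, attach a directional criterion to the baseline-adjusted aggregate benefit before superiority is declared, for example a posterior probability of benefit of at least 0.975, or a one-sided 2.5% test. The joint test can stay as evidence on profile shape. The cost is power for late-onset benefit when week-0 CDAI is noisy or within-patient correlation is lower: Scenario 3 at n=21 with noisy week 0 gives about 0.62-0.64, against 0.73 for the stated rule and 0.88 for step 1 alone.
3. Re-run Table 10 under the corrected rule, and add one crossing scenario and one scenario with harm at every visit.

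The work is protocol and SAP wording plus a simulation re-run. No visit, assessment or patient is added.
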